8.3.6 PATIENT REPLACEMENT

The following guidelines will be used to determine when a patient can be replaced

- During the Monotherapy period in the Dose Escalation part of the study, if a patient who is not tolerating the assigned dose of NOX66, may be replaced with another patient, following a joint decision between the Investigator and Medical Monitor. A maximum of 3 replacements is allowed in each dose level in the Monotherapy period.
- If any patient withdraws consent during Monotherapy period or during Cycle 1, he/she will be replaced with another patient.
- If any patient who has not taken at least 80% of the prescribed daily doses of NOX66 during Monotherapy period and Cycle 1, will be replaced with another patient.
- During the Dose Expansion Part, patients who have not completed at least 2 complete cycles of treatment, will be replaced with additional patients, until at least 12 patients have completed 2 cycles.

The recommended phase 2 dose (RP2D) may be defined as the highest dose of the combination administered if no DLTs are observed and the dosage form is acceptable to patients.

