----------------------	--

level. The previous dose level will then be considered for expansion to 6 patients in order to confirm that it is the MTD level. The MTD is defined as the dose level at which no more than 1 patient out of 6 experienced a DLT up to the end of Cycle 1. If in the first group at 800 mg daily (Cohort 1), 2 or 3 patients develop DLTs, then that dose level is considered to be the DLT level and 3 additional patients need not be tested at that level, but lower doses should be studied.

If no DLT is observed at 1800 mg (Cohort 3), dose escalation will be stopped. The proposed highest dose level (1800 mg) will be declared the MTD, and additional patients will be enrolled, if necessary, to ensure that a total of 6 patients are evaluated at this dose level.

The dose escalation scheme is presented in the following table.

Proposed Starting Dose and Dose Escalation Scheme for NOX66

Cohort	1	2	3
Increment	NA	50%	50%
Total daily dose (mg)	800	1200	1800
Daily regimen (mg)	400 BID	600 BID	600 TID

BID = twice daily, TID = three times daily. For each cohort, safety/tolerability and PK data will be collected on Days 1-2 and 7-8 for respective doses.

Assessment of toxicities and decisions about dose escalation and cohort expansion will be made by a Safety Review Committee, that will include at least one Sponsor representative participating investigators, and may also include a cardiologist or other outside consultants at the Sponsor's discretion.

Assessment of DLTs

Patients who withdraw in Cycle 1 for reasons other than safety or toxicity will be replaced. During the 7-day Monotherapy Period, any patient who develops a significant toxicity, as noted below, will be replaced.

For determination of DLT during Cycle 1, toxicity will be graded using the National Cancer Institute-Common Terminology Criteria for Adverse Events (NCI-CTCAE) Version 5.0. Any of the following, if judged to be associated with NOX66 alone or in combination with doxorubicin (i.e., possibly-, probably-, or definitely related to), will be considered a DLT:

- 1) Grade 3 non-hematological toxicities (excluding alopecia) with the following exceptions:
 - i. Grade 3 nausea/vomiting or diarrhea <72 hours with adequate antiemetic and other supportive care
 - ii. Grade 3 fatigue <1 week
 - iii. Grade 3 electrolyte abnormality that lasts 24 to 72 hours (Investigator's discretion for timeframe), is not clinically complicated

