8.3 DEFINITION AND DETERMINATION OF MTD AND DLT

8.3.1 DEFINITION OF MTD

The MTD is defined as the maximum dose level at which no more than 1 patient out of 6 experienced a DLT at the end of Cycle 1.

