8.3.5 EVALUABLE PATIENT

The criteria for determination of an evaluable patient for a dose escalation decision or determination of MTD, must include:

- Patient who experienced a DLT during the 21-day combination treatment cycle (Cycle 1) or
- Has not experienced a DLT and has taken at least 80% of the prescribed daily doses of NOX66 and completed all safety evaluations required in Cycle 1

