10.2.3 DOSE MODIFICATIONS

The dose of doxorubicin can be reduced from 75 to 60 mg/m² if a Grade 2 toxicity related to doxorubicin occurs. If serum bilirubin is 1.2-3.0 mg/dL prior to a cycle, a 50% dose reduction of doxorubicin is recommended. If serum bilirubin is 3.1-5.0 mg/dL prior to a cycle, a 75% dose reduction of doxorubicin is recommended.

If a perineal and/or anal rash develops (Grade 1-2), a topical hydrocortisone containing haemorrhoid cream/ointment and/or cutaneous cream should be used. For Grade 3-4 perineal and/or anal rash, NOX66 treatment should be delayed until the rash resolves to Grade 1 or completely. NOX66 should also be delayed if there is proctitis, rectal mucositis, or ulcer of Grade 2 or higher. Treatment may be resumed when toxicity decreases to Grade 1. Treatment with NOX66 should also be delayed in the presence of anorectal infections and may be resumed after they are resolved.

All dose delays for NOX66 and doxorubicin need to be discussed with the Medical Monitor.

For patients developing neutropenia, the following guidelines should be used for doxorubicin dose modification.

Toxicity	Recommended Dose Modification
ANC < 1,000	No doxorubicin administered; treatment cycle delayed
≥ Grade 3 neutropenic fever/infection	Approximately 60 mg/m ² doxorubicin
≥ Grade 4 neutropenia lasting longer than 1 week	Approximately 60 mg/m ² doxorubicin
Second incidence of either: 1) ≥ Grade 3 neutropenic fever/infection 2) Grade 4 neutropenia lasting longer than 1 week	Second dose reduction to 45 mg/m ²
Reversible Grade 3 neutropenia with fever/infection or Grade 4 ANC	Retreatment with doxorubicin at Investigator's discretion

Abbreviation: ANC = absolute neutrophil count

In the event of cardiac toxicity (e.g., if there is an absolute decrease in LVEF of >10% from the previous evaluation, or if the actual LVEF decreases to ≤40%) doxorubicin must be discontinued. Doxorubicin must also be discontinued if the patient develops Grade 3 or 4 left ventricular systolic dysfunction (symptomatic congestive heart failure).

Patients who discontinue doxorubicin after 4 cycles of treatment should complete the remaining 2 cycles of NOX66 as planned. If doxorubicin is discontinued prior to 4 cycles, NOX66 treatment may continue in consultation and agreement with the Medical Monitor.

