15.2.2.2 Safety Considerations for Dose Escalation

In addition to monitoring patient's safety throughout the study period, the Medical Monitor and Investigator will participate in the SRC meeting to assess cumulative safety data available on all

patients who had received at least 80% doses to determine whether dose escalation may occur according the prespecified rules in Section [8.1.1](#)

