15.2.2.3 Safety Pause and Prompt AE Review

If a DLT occurs in 1 patient in a cohort of 3 patients at a given dose level of NOX66 + doxorubicin, then 3 more patients should be enrolled at that same dose level. If a DLT is not observed in the additional 3 patients, the next cohort of 3 new patients may be enrolled at the next higher dose level.

If DLT occurs in 2 patients in a cohort of 6 patients at a given dose level, then this dose level will be defined as the DLT dose level. All Investigators will be informed, no additional patient(s) will be enrolled at the DLT dose level, and dose-escalation will stop. No more than 6 patients should be enrolled at the DLT dose level.

The dose for the next cohort will be determined at the SRC review meeting to evaluate all the available safety (including AEs that are not DLTs).

When a DLT occurs, the site must immediately inform the CRO who will then inform the other sites that a DLT has occurred and evaluate if a second DLT has occurred at any other sites. If 2 or more DLTs occur at the same dose level, further enrollment of new patients at that dose level or higher across all sites will be suspended until the SRC meeting occurs to evaluate if the MTD has been exceeded. To be included in a dose-escalation decision or determination of MTD, an evaluable patient is defined as one who either experienced a DLT during the first 21-day treatment cycle (Cycle 1) or has not experienced a DLT and has taken at least 80% of the prescribed daily doses of NOX66 of the monotherapy period and the first 21-day treatment cycle and completed all safety evaluations required in Cycle 1.

Due to the potential for Cycle 1 discontinuations, patients withdrawing for reasons other than safety will be replaced.

When a dose escalation is stopped, the patients treated at lower doses can continue as planned.

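### The 80% dosing rule replaces escalation patients whatever the cause, so patients under-dosed by NOX66 toxicity below the DLT threshold can drop out of the escalation and MTD count

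*Combined protocol and SAP*

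**What the plan says.** **Replacement.** Section 8.3.6 provides that an escalation patient who "has not taken at least 80% of the prescribed daily doses of NOX66 during Monotherapy period and Cycle 1, will be replaced". No cause is named. The same section caps replacements at three per dose level in the monotherapy period and gives no cap for Cycle 1.

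**Evaluability.** Under Section 8.3.5 a patient counts toward escalation or the MTD if a DLT occurred in Cycle 1, or if the patient "Has not experienced a DLT and has taken at least 80% of the prescribed daily doses of NOX66" and completed the Cycle 1 safety evaluations. Section 15.2.2.3 repeats this with a wider window: "has taken at least 80% of the prescribed daily doses of NOX66 of the monotherapy period and the first 21-day treatment cycle".

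**MTD.** Section 8.3.1 uses DLT counts alone: "The MTD is defined as the maximum dose level at which no more than 1 patient out of 6 experienced a DLT".

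**Dose delays.** Section 10.2.3 states that "NOX66 should also be delayed if there is proctitis, rectal mucositis, or ulcer of Grade 2 or higher", and also delays NOX66 for anorectal infection. In Section 8.3.3, non-hematological DLTs begin at Grade 3, with short-lived Grade 3 nausea, vomiting, diarrhea and fatigue exempt. No DLT item covers doses missed because of toxicity.

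**Withdrawals.** The Synopsis says "Patients who withdraw in Cycle 1 for reasons other than safety or toxicity will be replaced". Section 15.2.2.3 says "patients withdrawing for reasons other than safety will be replaced".

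**Escalation review.** Section 15.2.2.2 describes cumulative safety data on "patients who had received at least 80% doses to determine whether dose escalation may occur". Section 15.2.2.1 refers to all data, and Section 15.2.2.3 includes adverse events that are not DLTs.

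**The concern.** The 80% rule makes sense as a compliance filter: a patient who took little drug says little about its tolerability. The reasoning reverses when the doses were missed because of the drug. Such a patient is informative about whether the level can be taken, yet leaves both the numerator and the denominator of the rule that decides escalation.

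The plan creates such patients itself. A site that follows Section 10.2.3 for a Grade 2 rectal event may thereby make the patient non-evaluable. Estimating the MTD is a primary objective, and 16 expansion patients are then enrolled at that dose.

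The rules also disagree. Take a patient who withdraws in Cycle 1 for sub-DLT toxicity, having taken less than 80% of doses. The Synopsis and Section 15.2.2.3 imply no replacement; Section 8.3.6 orders it. For a patient who stays on study with doses missed, the withdrawal wording does not apply and Section 8.3.6 stands alone.

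**Working it through.** **1. The plan's own figures.** Escalation maximum: 3 levels × 6 = 18. Total: 18 + 16 = 34. Minimum: 3 + 3 + 6 + 16 = 28. These match the Synopsis and Section 14.1. The plan gives no operating characteristics for the escalation rule, so there is no pass probability to reproduce.

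**2. How many missed doses trigger replacement.** NOX66 is given for 7 days per period, two or three times daily (Section 10.2.1).

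| Window | Regimen | Doses | 80% of doses | Needed | Misses that trigger |
|---|---|---|---|---|---|
| Cycle 1 alone | BID | 14 | 11.2 | 12 | 3 |
| Cycle 1 alone | TID | 21 | 16.8 | 17 | 5 |
| Monotherapy + Cycle 1 | BID | 28 | 22.4 | 23 | 6 |
| Monotherapy + Cycle 1 | TID | 42 | 33.6 | 34 | 9 |

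On the first reading, less than two days of missed dosing is enough. On the pooled reading, a patient with complete monotherapy must miss three full days. Under pooling, a patient who misses 3 to 5 BID or 5 to 8 TID doses in Cycle 1 is not replaced but stays evaluable and counts as DLT-free.

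**3. Illustration of size.** Let d be the probability of a listed DLT and q the probability of falling below 80% through NOX66 toxicity without a listed DLT. Neither is in the documents; both are assumed. Under Section 8.3.2 a level passes with 0 of 3 DLTs, or with 1 of 3 followed by 0 of 3:

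P(pass) = (1−p)³ + 3p(1−p)⁵

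- As written, with replacement until evaluable: p = d/(1−q).
- Extreme bound, every such patient counted as an event: p = d + q.

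For d = 0.10:

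| q | p as written | Pass as written | p bound | Pass at bound |
|---|---|---|---|---|
| 0.10 | 0.111 | 88.7% | 0.20 | 70.9% |
| 0.20 | 0.125 | 86.2% | 0.30 | 49.4% |
| 0.30 | 0.143 | 82.8% | 0.40 | 30.9% |

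Example, q = 0.30 as written: 0.857³ + 3 × 0.143 × 0.857⁵ = 0.630 + 0.198 = 0.828.

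**4. Sensitivity.** At q = 0.30, moving d from 0 to 0.20 takes the as-written figure from 100% to 52.4% and the bound from 49.4% to 17.2%. Section 12.1 allots nine patient numbers per cohort. If nine is a hard limit and an unfinished cohort does not pass, the as-written figures for d = 0.10 become 88.6%, 84.6% and 77.2%. The gap depends on the assumed rates; its direction does not.

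**The case against.** **The SRC can already act.** It may repeat a level, wait for data or take other steps (Section 8.1.1). It adjudicates the MTD and considers tolerability (Section 15.2.1), and it can weigh non-DLT events (Section 15.2.2.3). Acceptability of the dosage form enters the RP2D. A reader might infer from Section 15.2.2.2 that the committee is barred from seeing under-dosed patients; the other sections do not support that. What stands against the plan is that these powers are discretionary, and none says how a replaced patient is to be considered.

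**The MTD is defined by DLTs.** A reader might infer that the MTD is biased upward. On the plan's own definition it is not: with d = 0.10 a level passes 90.6% of the time when q = 0, so replacement makes passing slightly harder. Patients with a DLT count whatever their intake, and most related Grade 3–4 non-hematological events are DLTs. The gap concerns sub-threshold or exempted toxicity, and the bound applies a different event definition. This objection stands and limits the claim.

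**A delay need not forfeit doses.** Section 10.2.3 allows resumption and requires delays to be discussed with the Medical Monitor. It does not say whether delayed doses are made up or still count as prescribed. The mechanism needs them to be lost.

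**No source for frequent local intolerance.** A reader might suppose it is the likeliest way for a suppository to fail. The NOX66-related events named in Section 6.1, at up to 1200 mg daily, are fatigue, dry mouth, oral mucositis and stomatitis, not anorectal events. The 1800 mg level is described as not previously evaluated. The 10 to 30% range is therefore illustrative only.

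**Replacement for intolerance is partly deliberate.** The Synopsis and Section 8.3.6 openly replace patients who cannot tolerate monotherapy. That is so, but it does not explain Cycle 1, where the withdrawal wording points the other way.

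**Conclusion.** The point holds in a limited form. As written, a patient whose doses are lost to NOX66 toxicity below the DLT threshold can be replaced and leave the escalation and MTD count. Section 8.3.6 does not agree with the Synopsis and Section 15.2.2.3 on safety-related non-completers. Section 15.2.2.2 does not agree with Sections 15.2.2.1 and 15.2.2.3 on whose data the SRC reviews. The 80% window is undefined.

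These textual findings need no assumption beyond delayed doses being lost. The size does: 89, 86 and 83% as written against 71, 49 and 31% rests on assumed rates and on treating every such patient as an event, so it marks the outer limit of the effect and not its expected value.

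A reader might go further and conclude that these patients must count toward the two-of-six limit. The documents do not support that; it would in effect rewrite the DLT rule.

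**What to change.** - Reconcile Sections 8.3.5, 8.3.6, 15.2.2.2 and 15.2.2.3 with the Synopsis, so that below-80% replacement applies only to doses missed for reasons unrelated to study-drug toxicity. Say how this fits with the separate monotherapy replacement provision.
- Keep patients under-dosed because of at least possibly related toxicity in the cohort data, and present each to the SRC before any escalation or MTD decision.
- Have the SRC review all treated patients, with dose intake and reasons for missed doses.
- State whether 80% is judged per period or pooled, and whether delayed doses count as prescribed doses not taken.
- Leave it to the sponsor and SRC to specify in advance, in the protocol or SRC charter, how such patients count toward the MTD limit.

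The change is to protocol and charter wording. The cost is that some cohorts may need more patients, or escalation may stop earlier.

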9 STUDY PARTICIPANTS

9.1 STUDY POPULATION

Up to approximately 34 patients with metastatic STS will be studied. Patients will be selected at cancer centers that have a sufficient number of sarcoma patients who would be willing to participate in clinical trials, and the center is equipped to provide rapid, comprehensive

treatment for different types of sarcoma. The Investigators chosen for this study must have expertise in the treatment of sarcoma as well as in the administration of doxorubicin.

9.2 INCLUSION CRITERIA

Patients must satisfy all of the following criteria to be included in the study:

1. Adult patients (≥ 18 years of age, inclusive at the time of signing the informed consent) with histologically confirmed diagnosis of metastatic or recurrent STS (histopathology, i.e., type of sarcoma and grade needs to be recorded).
2. Patients for whom treatment with doxorubicin is considered to be appropriate (hemoglobin > 10 g/dL, ANC $> 1000/\mu\text{L}^3$, and platelets $> 100,000/\mu\text{L}^3$), serum bilirubin $< 1x$ the institutional upper limit of normal (ULN) (unless known Gilbert's disease), AST or ALT $< 3x$ institutional ULN, and creatinine clearance ≥ 50 mL/min as determined by the Cockcroft-Gault equation. The laboratory normal ranges for clinical laboratory tests must be sent to the Sponsor/CRO before the study is initiated at each site.
3. Left ventricular ejection fraction $\geq 50\%$.
4. Disease that is considered measurable according to RECIST v1.1.
5. Eastern Cooperative Oncology Group (ECOG) performance status of 0–2.
6. Anticipated life-expectancy of at least 6 months.
7. For females of reproductive potential the following are considered highly effective acceptable forms of contraception: surgical sterilization (tubal ligation); total abstinence from sexual intercourse with the opposite sex; established hormonal birth control (e.g., oral, transdermal, injection, or implant) plus a barrier method or a double barrier method (intrauterine device, spermicide, or diaphragm plus condom) for at least 1 month prior to screening and agreement to use such a method during study participation and for an additional month after the last dose of NOX66 or 6 months after the last dose of doxorubicin, whichever is longer.
8. For males of reproductive potential: vasectomy or use of highly effective contraception (e.g., condoms, abstinence) during the study and until 3 or 6 months after the last dose of NOX66 or doxorubicin, respectively, whichever is longer.

9.3 EXCLUSION CRITERIA

Patients who meet any of the following criteria will be disqualified from entering the study:

1. Histologically or cytologically confirmed Kaposi's sarcoma, gastrointestinal stromal tumor (GIST), extra-skeletal myxoid chondrosarcoma, epithelioid hemangioendothelioma, and desmoid tumor.
2. Hepatic impairment defined as serum bilirubin $> 1x$ ULN (unless known Gilbert's disease) or either AST or ALT $> 3x$ institutional ULN.
3. Unstable angina pectoris, angioplasty, cardiac stenting, or myocardial infarction 6 months before study entry.
4. Untreated metastases to the CNS.
5. Received previous treatment with anthracyclines and anthracenediones.

6. Previous radiation therapy to the mediastinal or pericardial area.
7. A known allergy to any of the treatment components.
8. Active or chronic infection with human immunodeficiency virus (HIV). NOTE: Patients with chronic HIV infection, on ongoing treatment with anti-viral medications, who have an undetectable viral load are not considered to be infectious and can be included in this study.
9. Pregnant (positive urine pregnancy test) or lactating.
10. Patient not willing to use suppositories.
11. Patients with a colostomy.
12. Patients who have had a colectomy (total or left hemicolectomy) with re-anastomosis
13. Patients for whom administration of the suppositories are likely to cause pain (e.g., inflamed hemorrhoids, fissures, or lesions of the anus or rectum).
14. Patients with fecal impaction, chronic idiopathic constipation, or chronic diarrhea or alternating irritable bowel disease.
15. Patients with inflammatory bowel disease (e.g. Crohn's disease or ulcerative colitis).
16. Previous treatment with an investigational agent or the non-approved use of a drug or device within 4 weeks before study entry.
17. Uncontrolled diabetes mellitus.
18. Patients who require concomitant use of inhibitors or inducers of CYP3A4, CYP2D6 or P- glycoprotein (P- gp).

9.4 STUDY WITHDRAWAL CRITERIA

Patients will be withdrawn from the study if any of the following occurs;

- Patient withdraws consent
- Death

9.5 TREATMENT WITHDRAWAL CRITERIA

Treatment with NOX66 or doxorubicin will be withdrawn if one or more of the following occurs:

- Disease progression based on RECISTv1.1
- An inter-concurrent illness that prevents further administration of NOX66
- An adverse event that is intolerable to continue the treatment with NOX66 and doxorubicin or any DLT (Section 8.3) that has not resolved to Grade 1.
- Cardiac toxicity, e.g., if there is an absolute decrease in left ventricular ejection fraction (LVEF) of >10% from the previous evaluation, or if the actual LVEF decreases to ≤40%, requires doxorubicin to be discontinued. Doxorubicin must also be discontinued if the patient develops Grade 3 or 4 left ventricular systolic dysfunction (symptomatic congestive heart failure).
- Any other reason the Investigator considered that impacts the patient's safety.

In all cases, the reason for study or treatment withdrawal, either at the patient's request or at the Investigator's discretion, and the date of last dose of NOX66 and doxorubicin, must be recorded in the electronic case report form (eCRF) and in the patient's medical records. The patient must be followed to establish whether the reason was an adverse event causally related to NOX66, and, if so, this must be reported in accordance with the procedures in Section 11.3.

Any patient who appears to be noncompliant should be counselled but not withdrawn from the study in Cycles 2 to 6.

